#### **4.7. Total number of devices intended for the clinical investigation**

Each subject will be supplied with one CLINY Self-Catheterization Set, and cleansing products as described below:

1 CLINY Self-Catheterization Set:

- 1 catheter case with a cap
- 1 outer case
- 1 bottle of Milton cleansing solution
- Optilube, sterile lubricating gel

In case of a damaged or missed CLINY catheter, the subject will be distributed a new CLINY Self-Catheterization Set from site. Sponsor must be reported if a replacement of a new CLINY Self-Catheterization Set is needed, and the replacement must be reported in the eCRF. The replaced CLINY as well as the new CLINY must be collected by the site and sent for laboratory assessments by the end of use.

To ensure that the site has enough supplies, more products than needed will be provided by sponsor to the site. All products will be accounted for both prior and after use.

### **5. Design of the clinical investigation**

#### **5.1. General**

The investigation is designed as an open-labelled, single-arm investigation, in which the reuse CLINY catheter will be compared to single use catheters at baseline.

The study design includes an initial evaluation of a cohort of catheter users who currently practice hydrophilic single use clean intermittent catheterization. The cohort will be followed for 4 weeks (28 days) when switching to multiple reuse catheters.

The test period of 4 weeks will consist of up to 3 site visits and 3 phone visits within a 4-week test period. Subjects using single use catheters for bladder management will use one distributed CLINY Self-Catheterization Set during the test-period. The expected duration of the total test-period is 28 days.

In total, 40 subjects will be included in the investigation. Each subject will undergo a Screening Visit (V0), a Baseline Visit (V1), 3 phone calls (V2, V3 and V4) and a Termination Visit (V5) carried out by the Principal Investigator (PI), or delegate. Visit 0 and 1 can be performed on the same day.

At a scheduled Screening Visit (V0), the subject will be verbally informed about the investigation, where the PI or delegate will give information about the investigation, the content and what it involves when participating in the investigation and the eligibility criteria. This information can be performed as a phone call if needed and the subject will be distributed a Subject Information Form/Informed Consent Form/ (SIF/ICF) by mail.

At the scheduled Baseline Visit (V1), the subject receives additional information if needed and the in- and exclusion criteria will be reviewed. See section 6.2 for recruitment and enrolment.

The Screening Visit (V0) and Baseline Visit (V1) can be performed the same day.

If the subject wishes to reconsider his/her participation at V0 after another oral review of the content of the investigation, the subject has the rights to wait minimum 24 hours before deciding on participation. If the subject hereafter decides to participate in the clinical investigation a V1 will be scheduled unless performed the same day as the Screening Visit (V0).

The subject is included in the investigation upon signed informed consent at the Baseline visit (V1). The Baseline Visit (V1) can be conducted at the latest, 3 days after V0.

At V1, all baseline information will be collected by the PI or delegate (see flow chart, Table 5).

The subject will complete questionnaires on a paper form and the investigator or delegate will report the assessments in an electronic data base, electronic Case Report Form (eCRF).

The subject will be instructed in use of the investigational test product, CLINY Self-Catheterization Set, according to the IFU (Appendix A).

A phone call (V2) will be conducted 7 days (+/- 1 day) after V1, a phone call (V3) will be conducted 14 days (+/-1 day) after V1, and a phone call (V4) will be conducted 21 days (+/-1 day) after V1.

At the time of the phone calls the subject will be reminded of the instructions for using the investigational device, CLINY Self-Catheterization Set, review of AE's, review concomitant medication, evaluate use of single use catheters (protocol deviations), average number of daily catheterizations with CLINY and results of a same day urine dipstick will be assessed as well. The investigator or delegate will report the assessments in the eCRF.

The Termination Visit (V5) will be conducted 28 days (+3 days) after V1 unless a situation occurs where a subject terminates earlier than expected. If this is the case the subject will as the last visit have the termination visit performed (V5) including all assessments in Visit 5.

The subject will bring the used CLINY Self-Catheterization Set at the Termination Visit, and the PI or delegate will collect the used CLINY Self-Catheterization Set for laboratory analysis. The subject will complete Termination Visit (V5) questionnaires in a paper form and the investigator or delegate will report the assessments in the eCRF.

**Figure 2: Design of the Clinical Investigation**

### 5.2. Primary endpoint

**Primary endpoint:**

- Health-related quality of life (HR-QoL) measured by intermittent self-catheterization questionnaire, (ISC-Q) index score at Baseline Visit (V1) and at the termination Visit (V5)

### 5.3. Secondary and exploratory endpoints

**Secondary endpoints:**

- Adverse events

**Exploratory endpoints:**

- Satisfaction of intermittent catheterization measured by the InCaSa questionnaire score
- Perception questions (evaluated on a 6-point scale)
- Total catheter-associated bacterial count (CFU/mL)
- Number of bacterial-positive catheter samples

See Appendix H for endpoints and assessments.

### 5.4. Rationale for selection and measurement of endpoints

The primary as well as part of the exploratory endpoints and assessments are subjective and have been selected as they are considered essential parameters to evaluate the effects of repeated reuse of catheters and for the observation on the impact of a switch from single use to reusable catheters.

To evaluate the primary endpoint HR-QoL, the ISC-Q questionnaire will be applied. The ISC-Q is a newly developed and validated patient reported outcome questionnaire that evaluates aspects of quality of life specific to the needs of patients with neurogenic bladder disorders who perform CIC. The questionnaire consists of 24 items categorized in 4 domains, including ease of use, convenience, discreetness, and psychosocial well-being. Each item is rated on a 5-point Likert scale.

The secondary as well as part of the exploratory endpoints are objective and are essential to investigate the effects of repeated reuse of catheters and for the observation on the impact of a switch from single use to reusable catheters as well as to ensure safety.

To evaluate the exploratory endpoint, satisfaction of intermittent catheterization, the InCaSa Questionnaire will be applied (InCaSa-Intermittent Catheterization Satisfaction Questionnaire).

### 5.5. Demography and potential compromising factors

The following baseline data will be collected and reported at the Baseline Visit (V1) by the investigator or delegate:

- Date of informed consent
- Date of visit
- Age
- Height (in cm)
- Weight (in kg)
- Gender (Male/Female)
- Concomitant medication
- Reason for using intermittent catheterization
  - Spina cord injury
  - Multiple sclerosis
  - Spina Bifida
  - Benign Prostatic Hyperplasia
  - Others (text)
- When did you start using a catheter? (months/years)
- Current single use catheter (at time of enrolment)
  - Brand
  - Product name
  - Item number
- Single use catheter size at time of enrolment
- Average number of catheters used per day during the last 1 month
- Time spent on each catheterization from preparation to storage/disposal (in minutes)
- Handedness
- Urethral sensation
- Hand dexterity

### 5.6. Equipment/methods and timing for assessing the variables

The primary endpoint is evaluation of HR-QoL assessed at Baseline Visit (V1) based on use of the single use intermittent catheterization and assessed after 28 days at Termination Visit (V5) based on use of the reuse catheter. HR-QoL will be measured by the ISC-Q index score.

The secondary endpoint will be an evaluation of adverse events from time of signed informed consent and throughout the test period.

The exploratory endpoints will be collected with satisfaction questionnaire score and perception questions at visit 1 and visit 5.

Evaluation of intermittent catheterization satisfaction assessed at Baseline Visit (V1) and after 28-days of using the re-use catheter CLINY, at the Termination Visit (V5). For this assessment the InCaSA – Intermittent Catheterization Satisfaction Questionnaire will be used.

Evaluation of intermittent catheterization related to perception will be assessed at Baseline Visit (V1) and after 28-days of using the reuse catheter CLINY, at the Termination Visit (V5). For this assessment, perception questions on a 6-point scale will be used for measuring of this endpoint.

Evaluation of total catheter-associated bacterial count and number of bacterial-positive catheter samples:

In a laboratory at Coloplast the total catheter-associated bacteria count (CFU/mL) will be assessed for all CLINY catheters collected at Termination Visit (V5). The number of bacterial-positive catheter samples will also be assessed, where positive is defined as presence of any detectable concentration. The data will be compared to a baseline evaluation of the CLINY catheter-associated bacterial count and number of bacterial-positive catheter

samples. In total 6 single use hydrophilic coated catheters taken directly from packages will be assessed, thus no bacteria are expected on the samples.

See Flowchart table 5 for further information regarding timing of endpoint data capture.

### **5.7. Blinding**

(Not applicable)

### **5.8. Total expected duration of the clinical investigation**

The dates below are approximate, and no subjects will be enrolled before all required approvals have been obtained. If changes are required, EC will be notified.

- First subject enrolled (06/2022)
- Last subject enrolled (02/2023)
- Last subject completed (03/2023)
- Final report (04/2023)

## **6. Clinical Investigation population**

The clinical investigation will be conducted in 40 subjects enrolled in multiple clinical investigation sites. The enrolment is competitive.

To allow for statistically significant data, a minimum of 20 eligible completed subjects in multiple clinical investigation sites will be adequate for obtaining indications on the effects of repeated reuse of catheters, hence the aim for this investigation is 20-40 completers.

Considering a drop-out rate of 50 %, the total number of subjects to be enrolled must be 40.

Recruitment and discontinuation will be followed very closely, and all replacements evaluated on an ongoing basis depending on both number of discontinued subjects and the time the subjects participated in the investigation. As a minimum sponsor will make a status on the recruitment strategy every month or at least when half of the subjects have been recruited.

The aim is to keep the LPO date. If concerns of high dropout rate recruitment/retention arise and status will be discussed by sponsor.

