### 6.2. Recruitment and enrolment

Recruitment of potential subjects will begin once approval have been obtained from the Ethics Committee (EC). It is estimated that the recruitment process will be completed within 6 months.

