#### **6.4. Point of enrolment**

A subject is considered enrolled in the investigation when the written informed consent is obtained. The expected duration for each subject is described in Section 5.1 General.

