### 15.4. Financial conditions

Coloplast A/S will compensate all investigators involved in the clinical investigation for their time and resources spent on the investigation. All financial agreements with the investigation sites involved in the clinical investigation will be specified in a sponsor investigator agreement.

The expenses include the salary to the Principal Investigator, the cost of external clinical support, study supplies, eCRF, Investigator and site personnel training and patient expenses including travel expenses.

The Principal Investigator and site personnel have no financial interests in the investigation.

The total budget for the investigation is [REDACTED] covering 40 participants. The expenses are paid on an ongoing basis.

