## 22. Suspension/termination of the clinical investigation

Sponsor will withdraw from sponsorship of the clinical investigation if

- major non-adherence to the clinical investigation plan is occurring
- it is anticipated that the subject recruitment will not be adequate to meet the investigation objectives at least 75% of the subjects should be entered within the recruitment time.

In case sponsor withdraws, sponsorship for the subjects already recruited into the clinical investigation will continue.

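### Do the recruitment and replacement rules undercut the plan's own minimum of 20 completers?

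*Combined protocol and SAP*

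**What the plan says.** Section 6 states its adequacy criterion in completers: "To allow for statistically significant data, a minimum of 20 eligible completed subjects in multiple clinical investigation sites will be adequate for obtaining indications". It gives the aim as 20 to 40 completers and derives the enrolment figure from it: "Considering a drop-out rate of 50 %, the total number of subjects to be enrolled must be 40." Section 5.1 repeats the total of 40. Section 10.5 says that no formal sample size calculation was made and mentions an earlier study with 37 completers as a precedent.

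Three other rules bear on this figure.

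- **Recruitment floor (section 22).** The sponsor withdraws from sponsorship if it expects that recruitment "will not be adequate to meet the investigation objectives at least 75% of the subjects should be entered within the recruitment time".
- **Replacement (sections 6, 6.3 and 10.5).** A subject who chooses to stop before day 14 has to be replaced, with the sponsor's agreement. Other replacements are at the sponsor's discretion and are kept under review according to how many subjects stop and how long they took part. Section 6.4 fixes when a place is used: "A subject is considered enrolled in the investigation when the written informed consent is obtained". Section 15.4 describes the budget as "covering 40 participants. The expenses are paid on an ongoing basis".
- **Recruitment time.** Section 6.2: "It is estimated that the recruitment process will be completed within 6 months". Section 5.8 runs from June 2022 to February 2023 for first and last enrolment, about 8 months.

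**The concern.** The minimum is counted in completers, while the rule for judging recruitment counts subjects entered. If 75% of 40 is taken as good enough, the plan's own drop-out figure predicts a shortfall against its own minimum. Even the full 40 has no margin, because 20 is the expected number.

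The replacement rule could supply a margin, but the plan does not say whether a replacement takes one of the 40 places or adds to them. Since a place is used at consent, the first reading adds nobody. The second goes beyond the stated total and the budgeted number. Sites, budget holder and ethics committee could therefore be working to different enrolment totals, and the sponsor could regard recruitment as adequate when 20 completers are unlikely.

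**Working it through.** **Inputs.** Minimum 20 completers, drop-out 50% and enrolment 40 (section 6); floor 75% (section 22); replacement before day 14 (sections 6.3 and 10.5). Two assumptions are added: drop-outs are independent, and a share *s* of them falls before day 14. The documents give no value for *s*, so 25%, 50% and 75% are shown.

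**1. The plan's figure.** 20/(1 − 0.50) = 40. Reproduced.

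**2. Chance of reaching the minimum, nobody added.** Completers ~ Binomial(*n*, 1 − drop-out). The floor is 0.75 × 40 = 30 entered.

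| Drop-out | 40 enrolled: expected | P(≥ 20) | 30 entered: expected | P(≥ 20) |
|---|---|---|---|---|
| 50% | 20 | 0.56 | 15 | 0.05 |
| 40% | 24 | 0.93 | 18 | 0.29 |
| one third | 26.7 | 0.99 | 20 | 0.59 |

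Thirty entered give 20 on average only if drop-out is at most 1 − 20/30 = 33.3%.

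**3. Mandatory replacement on top of the 40.** If each early leaver is replaced until the place passes day 14, the completion probability per place is 0.5/(1 − 0.5*s*) and expected enrolment is 40/(1 − 0.5*s*).

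| *s* | Completion per place | Expected completers | Expected enrolled | P(≥ 20) |
|---|---|---|---|---|
| 25% | 0.571 | 22.9 | 45.7 | 0.86 |
| 50% | 0.667 | 26.7 | 53.3 | 0.99 |
| 75% | 0.800 | 32.0 | 64.0 | > 0.99 |

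So 0.56 applies if every drop-out falls on or after day 14, or if replacements are counted inside the 40.

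**4. What 50% means.** An aim of 20 to 40 completers from 40 enrolled corresponds to drop-out between (40 − 20)/40 = 50% and (40 − 40)/40 = 0%. On that reading 50% is the upper end, and the first row of the table in step 2 is the unfavourable edge.

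**5. Effect on the analysis.** Section 10.3 estimates the difference between catheters with a 95% confidence interval, and section 10.2 bases it on the full analysis set, not on completers. Under sections 5.1 and 10.5, subjects who stop early are asked to attend the termination visit with all its assessments, including the ISC-Q, so pairs can exceed completers. If they did not, 15 pairs instead of 20 would widen the interval by about √(20/15) = 1.15, ignoring the small change in the *t* quantile. Its validity would not change.

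**6. Whether a tighter rule would gain anything.** Two repairs suggest themselves.

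- *Replacements on top of the 40, capped at 48 enrolled.* P(≥ 20) becomes 0.84, 0.90 and 0.90 for the three values of *s*, against 0.86, 0.99 and above 0.99 uncapped. The cap lowers assurance, has no basis in the documents, overrides the replacement duty once reached, and still exceeds the budgeted 40.
- *A running projection of completers in section 22.* With *C* completers and *D* drop-outs so far out of *N*, the projection is *C* + (*N* − *C* − *D*) × *C*/(*C* + *D*) = *N* × *C*/(*C* + *D*). If the first subject with a known outcome is a drop-out, it equals zero, and the sponsor would be told to withdraw on the strength of one person.

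**The case for a change.** The strongest case for a change is that section 22 claims to test adequacy for the investigation's objectives, yet it would not be triggered at 30 entered, where the plan's own figures give a 5% chance of the stated minimum. Nor is 0.56 only a matter of drop-out timing: if replacements sit inside the 40, it holds whatever the timing, while the better figures need about 46 to 64 enrolled against a stated total and a budget of 40. Drop-outs from day 14 onward and withdrawals decided by the investigator carry no stated duty of replacement, and section 6 adds "The aim is to keep the LPO date", so extra time cannot be assumed.

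Three parts of this stand. The 75% is not tied to the 20 completers, the place of replacements in the count is unstated, and the two recruitment periods differ.

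The rest is weaker. Section 22 says when the sponsor leaves; it nowhere says that 30 is enough or that enrolment stops there, and sections 5.1 and 6 still call for 40. A replacement in the ordinary sense is an extra person. Section 6 follows the completion-date aim directly with discussion by the sponsor if drop-out is high, and it already requires close follow-up of recruitment and discontinuation, so a shortfall would be seen while it could still be acted on. The 6 months is an estimate and the section 5.8 dates are labelled approximate, which makes that difference clerical.

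**Conclusion.** The arithmetic of the concern is correct, but it does not call for a change. Forty enrolled at 50% drop-out gives 20 completers in expectation. The chance of at least 20 is 0.56 if nobody is added, and 0.86 to above 0.99 if the mandatory early replacements are additional and 25% to 75% of drop-outs precede day 14. The 0.05 belongs to stopping at 30 entered, which the plan does not adopt. These figures assume independent drop-outs; the early share is an assumption that the documents cannot settle.

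What is left is a gap in cross-referencing that the sponsor can fill sensibly through its existing review of recruitment and replacements. Sections 3.2 and 10.7 set no success or pass/fail criterion, so missing 20 would cost some precision and would not invalidate the estimate. The concrete repairs examined either lower assurance and exceed the budgeted number or create an erratic withdrawal trigger. A sentence on whether replacements are additional, and on the 75% being only a floor, would be harmless tidying; the analysis and its interpretation would be the same without it.

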## 6.1. Eligibility criteria

To be included in the investigation, the subjects must comply with the selection criteria described below

### 6.1.1. Inclusion criteria

Table 2: Inclusion criteria

Inclusion criteria	Justification
1. $\geq 18$ years of age and has full legal capacity	To meet Helsinki declaration
2. Signed informed consent form	To meet Helsinki declaration
3. Use clean intermittent catheterization to the greatest extent possible (at least three times daily) for at least the last 1 month prior to inclusion	To ensure subjects are familiar with CIC use
4. Self-catheterize using a single use hydrophilic coated catheter for at least 1 month prior to inclusion	To ensure subjects are familiar with CIC use
5. Ability (assessed by the investigator) and willingness to participate in a 4-week study period with at least three catheterizations a day using the investigational test product	To ensure sufficient data for successful completion of the investigation

### 6.1.2. Exclusion criteria

Table 3: Exclusion criteria

Exclusion criteria	Justification
1. Participation in any other clinical intervention study during this investigation	To eliminate unintentional effects from other devices/medicines on the investigation's data
2. Previous participation in this investigation	To ensure data are not recorded twice
3. Symptoms of UTI at time of inclusion, as judged by the investigator	To ensure safety and integrity of results
4. Any known allergies towards ingredients in the investigational device	To ensure safety and integrity of results
5. Antibiotic treatment within 2 weeks prior to the Baseline Visit (V1)	To ensure integrity of results
6. Pregnancy	Even though the ingredients and recipes have been approved for human beings, their effect on embryos, fetuses and infants are unknown
7. Breastfeeding	Even though the ingredients and recipes have been approved for human beings, their effect on embryos, fetuses and infants are unknown

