### Test products

The CP352 investigational device is the CE-marked CLINY reuse catheter (CLINY Self-Catheterization Set) which is a reusable catheter made of 100% silicone rubber to be reused for a maximum of 28 days before disposal.

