### 4.1. Description of the investigational device

The CLINY Self-Catheterization Set consists of four non-sterile parts:

- A foldable catheter case of polypropylene, silicone rubber (can be folded into a small size)
- A cap of polypropylene, silicone rubber
- A catheter of silicone rubber
- An outer case to carrying with the catheter case

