#### **7.5. Supplementary materials and equipment**

The investigational device must be used with a lubricating gel, and subjects will be supplied with Optilube, sterile lubricating gel, which is CE-marked. Furthermore, the catheter will be cleansed after use according to the IFU with a Milton cleansing solution (CE-marked), and subjects will be supplied with this as well.

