## Appendix A: IFU – CLINY Self-Catheterization Set

### Self-Catheterization Set

#### Instructions for use

##### [Warning]

[figure not shown]
This device must be used after it has been disinfected using an appropriate disinfectant of right concentration.  
[It is a non-sterilized product.]

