##### [Operation Procedure]

A typical operation procedure is described below:

- 1) Straighten the catheter case and fill the catheter case with a disinfectant of right concentration. See the following drawing as target amount of solution (Figure 1).

[figure not shown]

Figure 1

2) Push the cap into the funnel until the chase of the cap places at the second lib of the funnel in order to fix firmly. (Figure 2).

Figure 2

3) Straighten the catheter case and insert the catheter with cap into the catheter case. Turn the cap surely and lock it in firmly. And make sure that disinfectant is not leaked from the catheter case.  
 4) Pull out the catheter and take urination procedure.  
 5) After use, clean the catheter with tap water, boiling and so on. And then house and store it into the catheter case filled by disinfectant according to the steps 2) to 3) of [Operation Procedure].  
 6) After bending the catheter case and keep the bended form by hook, put it in the outer case.

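### The only allergy exclusion is tied to the investigational device, but the protocol contradicts itself on whether the mandatory gel and the cleansing solution belong to that device

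*Combined protocol and SAP*

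**What the plan says.** Allergy appears in one eligibility criterion: exclusion 4 of Table 3 (section 6.1.2), which is exclusion 3 in the synopsis. It rules out "Any known allergies towards ingredients in the investigational device". Table 3 justifies it on grounds of safety and of the integrity of the results.

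On what the device is:
- Section 4 names the CLINY Set as the investigational device. Section 4.1 states: "The CLINY Self-Catheterization Set consists of four non-sterile parts". These are the case, the cap, the catheter and the outer case, and the only materials named are polypropylene and silicone rubber. The synopsis describes the catheter as "a reusable catheter made of 100% silicone rubber to be reused for a maximum of 28 days before disposal".
- Section 7.5, on supplementary materials, says: "The investigational device must be used with a lubricating gel, and subjects will be supplied with Optilube, sterile lubricating gel". It adds that "the catheter will be cleansed after use according to the IFU with a Milton cleansing solution".
- Section 4.7 lists a bottle of Milton and the Optilube gel as bullets beneath a line reading one CLINY Set. The sentence introducing that list names the Set and the cleansing products as separate items.

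On use, the IFU in Appendix A warns: "This device must be used after it has been disinfected using an appropriate disinfectant of right concentration". It has the catheter stored in a case filled with disinfectant, and the next step is "Pull out the catheter and take urination procedure". Its table of disinfectants gives diluted Milton in the sodium hypochlorite row.

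**The concern.** The scope of the exclusion depends on the word device. If the device is the four parts in section 4.1, the criterion covers silicone rubber and polypropylene but neither of the two other products that the procedure brings into contact with the urethra. A person who knows of an allergy to one of them could then be enrolled without breaching any written criterion. If the device is everything in the section 4.7 list, the same person is excluded. With several sites recruiting, the rule could be applied differently from site to site.

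What is at stake is first the subject's safety, since the exposure would be foreseeable and avoidable. Second, adverse events are the only secondary endpoint, and Table 6 already anticipates urethral stinging and mucosal irritation as likely. A reaction to the gel or the disinfectant might be hard to tell apart from an effect of the catheter. The criterion's own justification applies to the supplied products as much as to the catheter.

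**Working it through.** The plan states no figure on this point, so the check is a comparison of texts plus one count.

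**Step 1. Are the gel and the solution part of the device?**

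| Place | Gel | Cleansing solution |
|---|---|---|
| Section 4.1, four parts | not among them | not among them |
| Section 7.5 | separate, supplementary | separate, supplementary |
| Section 4.7, introductory sentence | not mentioned | named apart from the Set |
| Section 4.7, bullets | under the Set | under the Set |
| IFU, list of materials | not listed | not listed |

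Most of the text puts both products outside the device; the bullets in 4.7 put them inside. Those bullets are a weak definition, because they do not list the catheter itself. They still contradict 4.1 and 7.5.

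**Step 2. Is exposure part of the procedure?** For the gel, yes: section 7.5 makes it compulsory. For the solution, the IFU requires disinfection before use and storage in disinfectant, and section 7.5 supplies Milton for this. The Termination Visit instruction in section 7.1, that the returned catheter be stored without Milton, fits with Milton being the routine storage fluid. The IFU steps list no rinse between taking the catheter out and using it, although the IFU calls its procedure typical, so this does not show that subjects never rinse.

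**Step 3. Minimum number of exposures.** Inclusion criterion 5 in Table 2 requires at least three catheterizations a day with the test product. The test period is 28 days.

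3 per day x 28 days = 84 catheterizations

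This is a lower bound for a subject who completes the period as planned. Subjects who stop early have fewer.

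**Step 4. Does another item close the gap?** The baseline data in section 5.5 and the V0 and V1 procedures in section 7.1 include no allergy history beyond the check of the criteria. Inclusion criterion 5 lets the investigator judge ability to take part, but its stated reason is sufficient data, and it does not mention allergy. The risks listed in section 8.2 are haematuria, mechanical trauma and UTI.

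**Step 5. Size.** No allergy rate for either product is given, so an expected number cannot be calculated. For scale only, one affected subject would be 1/40 = 2.5% of the planned enrolment.

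**The case against.** The strongest reply is that section 4.7 already answers the point: the device is the CLINY Set, the list puts Milton and Optilube under the Set, and so the exclusion covers both. This stands far enough to defeat the flat reading that such a person certainly passes eligibility. A reader might infer that from 4.1 and 7.5 alone, but the documents support only a contradiction about scope.

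Other replies have some force:
- The IFU precautions call for a disinfectant suited to the patient, leave its concentration to the physician's judgement in light of the patient's condition, and list agents other than hypochlorite. This is a partial safeguard for the solution. It is not an allergy check, and it does not cover the gel.
- Section 6.3 requires withdrawal if safety or wellbeing is compromised. That acts only after exposure.
- The consent pages and the labelling of the two products are not available here, so a warning or question about allergy may exist there. That cannot be judged, and it would not settle the wording of the criterion.
- Both products are CE-marked. So is the catheter, and it still has an allergy exclusion.
- An exclusion for known allergy cannot catch a sensitivity that first shows itself during the trial. This is correct and limits the benefit of the change.

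A reader might also infer that reactions to the gel or solution would be counted as device effects of re-use and so distort the secondary endpoint. The documents do not support that as a certainty. Sections 18.2 and 18.7 grade relatedness to the device, and the category of possible relation expressly allows for another product as the cause. Section 10.4 reports adverse events descriptively, with no test. Misattribution is possible, not established.

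**Conclusion.** The point holds as a contradiction in the documents that leaves the scope of the only allergy exclusion unclear. On the reading that 4.1 and 7.5 support, a candidate whose known allergy is only to the gel or to the cleansing solution meets no exclusion criterion, despite the repeated exposure counted above.

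The importance is minor. The conclusion assumes that 4.1 and 7.5 define the device more reliably than the bullets in 4.7, and that no other trial document asks about these allergies. The expectation that few candidates are affected is a judgement, since the documents give no rate. No effect on the ISC-Q analysis, the significance level or the sample size is shown. The case for acting is that the written rule may be narrower than its own justification, on a matter of subject safety, and is easy to put right.

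**What to change.** 1. Make sections 4.1, 4.7 and 7.5 agree on whether the lubricating gel and the cleansing solution are part of the investigational device.
2. Reword the existing exclusion in Table 3 and the synopsis so that it does not depend on that answer. For example: any known allergy to ingredients of the investigational device, the supplied lubricating gel or the supplied cleansing solution.

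The cost is one line of eligibility text in two places, the alignment of three sections, and the amendment steps in sections 12 and 15.1. It should exclude few candidates. No visit, assessment or analysis changes.
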